In Aim 2 we propose combining taVNS with protocol-based task-specific training (TST), which is a form of motor rehabilitation therapy that increases the functional use and control of a paretic extremity [17-20]. TST improves functional outcomes and also induces neurophysiological changes in the ipsilesional motor cortex measured by functional neuroimaging and cortical excitability. Combining taVNS with the already established TST may rapidly accelerate and enhance the benefits of TST alone in a targeted neuroplasticity approach.

AIM 1: Establish a motion-activated, closed-loop taVNS platform for post-stroke motor recovery.

Hypothesis: Individualized EMG recording during upper limb rehabilitation is feasible and will generate a robust, specific (<80%), and sensitive (>80%) motion signal to drive taVNS in a safe and automated fashion (n=5).

AIM 2: Determine target engagement and optimal taVNS dosing and effect size of taVNS-paired TST to improve upper limb motor recovery. **Hypothesis:** taVNS delivered to the left ear of chronic stroke patients will activate the vagal afferent network and will induce greater motor cortex BOLD activity in a paired motor task compared to unpaired and placebo stimulation. Pairing closed-loop taVNS with TST induces a targeted cortical neuroplasticity that facilitates the enhancement of TST effects in upper limb hemiparesis in chronic stroke patients. This open label exploratory study will determine safety, feasibility, and effect size to power future controlled trials (n=20).

IRB Number: «ID»

Date Approved «ApprovalDate»

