4.0 Study Endpoints

This table describes the data collected and the endpoints that will be utilized. The endpoints revolve around clinical assessments (scales administered by a therapist) at weekly increments and at follow-up (2 and 8 week follow-up). These outcomes include Fugl-Meyer Upper Extremity (FM-UE) assessment, Wolf Motor Function Test, Action Research Arm Test, and Motor Activity Log.

There will also be baseline and final kinematic assessments that will be used to track outcomes, however these are secondary measures.

More details about endpoints are described in the study design section.

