Participants will receive taVNS stimulation to their left ear via electrodes attached to the anterior wall of the outer ear canal (25Hz, 500us pulse width, 200% PT). This will not be a therapeutic dose of stimulation, but rather a test of fit, comfort, and closed-loop functionality of the system in development.

We will analyze the EMG data and use it to determine optimal EMG thresholding levels for an automated sensing algorithm to be applied in Aim 2.

This experiment is not intended to provide any benefit to the participant. This serves for a system development and refinement study. All participants in this aim will be able to enroll into Aim 2

Specific Aim 2 – Determine target engagement and optimal taVNS dosing and effect size of taVNS-paired TST to improve upper limb motor recovery (n=20)

Screening

[figure not shown]
Prospective participants will be individuals who had a stroke > 6months prior to contact and must meet the following criteria to participate in this study: 18-80 years old with an ischemic or hemorrhagic stroke that occurred at least 6 months prior; completed conventional rehabilitation therapy at least one month prior; Unilateral limb weakness with Fugl Meyer-Upper Extremity Scale score less than or equal to 58 (out of 66)

For more information on tVNS screening please see the uploaded tVNS screening form. Written informed consent will be obtained from all participants prior to participation in the experimental paradigm.

Study Design

After successful validation of the closed-loop taVNS system is established, Aim 1 participants will be offered the ability to enroll into the Aim 2 & 3 studies of this proposal (n=20), an open-label pilot trial exploring the use of taVNS-paired vs unpaired motor rehabilitation. The primary goal is to determine safety, feasibility, and effect size of this paired therapy.

Participants enrolled in this study will receive upper limb motor rehabilitation (3days/week for 4 weeks. 1 hour/session) by a trained occupational therapist who is part of the college of health

IRB Number: «ID»
Date Approved «ApprovalDate»

professions rehabilitation CORE.

Neuroimaging (baseline and final)

All scanning will be performed on a 3T Siemens TIM Trio (Siemens, Erlangen, Germany). High-resolution T₁-weighted anatomical images will be acquired for each participant. Diffusion kurtosis imaging (DKI) or diffusion tensor imaging (DTI) scans will also be acquired for each participant.

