Clinical Assessments: A therapist from the **QBAR CORE** will conduct weekly clinical assessments on all participants enrolled in this study, including at follow-up visits (2 & 8 weeks post-treatment). Fugl-Meyer Upper Extremity (FM-UE) assessment, Wolf Motor Function Test, Action Research Arm Test, and Motor Activity Log. Assessments will be video recorded and rated by the study's Treatment Occupational Therapist .

Overground Walking: Participants will walk indoors on and off a pressure-sensitive walkway at multiple

IRB Number: «ID»
Date Approved «ApprovalDate»

speeds, but we will not ask them to run or go faster than they feel comfortable and safe. The walkway measures the speed of walking and the size of steps. A physical therapist or trained assistant will walk beside participants across the walkway, and when possible, the participant will be attached to a mobile, ceiling-mounted safety support. They will be asked to walk several times across the walkway.

Treadmill Walking: We will test walking adaptability with a series of tasks. Participants will be asked to walk on a split-belt treadmill at varying speeds, but we will not ask them to run or go faster than they feel comfortable and safe. During all treadmill walking, participants will wear a harness attached to a device attached to the ceiling. This device can move with participants and will catch them and prevent a fall in case of a stumble or misstep. A therapist or trained assistant will stay along to provide any physical assistance participants may need.

Kinematics: Using resources in the **QBAR CORE**, a technician will perform brief kinematic assessments at baseline and immediately following the acute treatment phase of the rehabilitation training on both the affected and unaffected limb. Kinematics of hand and arm will be recorded using a motion capture system with 36 active markers and 10 cameras (PhaseSpace Inc., San Leandro, CA). We will capture movement during three specific tasks (reach, grasp, single joint movement) and quantify functional improvements comparing post-treatment kinematics to baseline as well as between affected and unaffected limbs.

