The physical activity involved with this study may contribute to temporary muscle soreness or fatigue. These are normal responses to exercise and generally disappear within 1-2 days. Rest periods will be incorporated into the testing and training procedures, but participants will also be allowed additional rest at any time they wish during testing. Assistance will be provided during activities of walking or transferring from one surface to another, including the use of a support harness during treadmill walking. Despite these safety measures, as with any walking activity, there is a risk that participants may lose balance, stumble, fall, and experience an injury. Heart rate and blood pressure will be monitored during testing. Vital signs will be monitored routinely (at least every five minutes of activity) to make sure participants do not have a poor response to activity.

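### Aim 2 includes overground and treadmill walking tests with an acknowledged fall risk, but no aim, hypothesis, named endpoint or schedule row uses gait

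*Protocol*

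**What the plan says.** Section 10.0 of the Protocol describes overground and treadmill walking under the Aim 2 collected measures. Of the first it says "The walkway measures the speed of walking and the size of steps". Of the second it says "We will test walking adaptability with a series of tasks", and then: "Participants will be asked to walk on a split-belt treadmill at varying speeds, but we will not ask them to run". Neither paragraph gives a visit or a number of sessions, and the treadmill paragraph names no variable to be recorded.

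Aim 2 in section 1.0 reads "Determine target engagement and optimal taVNS dosing and effect size of taVNS-paired TST to improve upper limb motor recovery", and section 10.0 adds: "The primary goal is to determine safety, feasibility, and effect size of this paired therapy". On endpoints, section 4.0 says "These outcomes include Fugl-Meyer Upper Extremity (FM-UE) assessment, Wolf Motor Function Test, Action Research Arm Test, and Motor Activity Log", with kinematics as secondary measures.

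Section 15.0 has its own paragraph on walking risks. It mentions temporary soreness or fatigue ("These are normal responses to exercise and generally disappear within 1-2 days") and, despite the precautions, states that "there is a risk that participants may lose balance, stumble, fall, and experience an injury".

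**The concern.** A procedure that carries risk is normally justified by the question it answers. Here the protocol states the risk and leaves out the question. Two consequences follow.

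First, the gait data may not be interpretable. No before-and-after comparison is guaranteed when neither a baseline nor a post-treatment visit is fixed.

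Second, safety is part of the primary goal. Section 13.0 sends any adverse event to the IRB and the DSMB and plans an interim safety review at 10 of the 20 participants. The protocol does not say that events arising in the walking tests will be shown apart from events of the stimulation or the arm training.

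**Working it through.** No figure in the plan needs reproducing and no calculation applies. The check is to follow each Aim 2 measure through the protocol.

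| Measure (section 10.0) | Linked to an aim or hypothesis (1.0, 3.0, 10.0) | In section 4.0 prose | Row in the schedule table (10.0) |
|---|---|---|---|
| Four clinical scales | Yes, upper limb recovery | Yes | Yes: days 0, 3, 6, 9, 12 and follow-up weeks 2 and 8 |
| MRI | Yes, target engagement | No | Yes: days 0 and 12 |
| Kinematics (hand and arm) | Yes, upper limb recovery | Yes, secondary | Yes: days 0 and 12 |
| Actigraphy (both arms) | Yes, upper limb activity | No | Yes: treatment phase and follow-up |
| Overground walking | No | No | No |
| Treadmill walking | No | No | No |

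1. **Aims.** Aim 1 builds the EMG-triggered system. Aim 2 concerns target engagement, dosing and upper limb recovery. Sections 3.0 and 10.0 also mention a third aim that is not set out, but section 3.0 ties it to upper extremity training. Gait: 0 of 2 stated aims.
2. **Endpoints.** The four named scales assess arm function, and the kinematic tasks are reach, grasp and single-joint movement. Gait: 0 of 4 named scales, and not part of the kinematics.
3. **Schedule.** The rows are MRI, clinical assessment, kinematics and actigraphy. Gait: 0 of 4 rows.
4. **Power paragraph (section 12.0).** It covers fMRI activation and task-specific training. Gait is not mentioned.
5. **Eligibility (section 5.0).** The motor criteria are a Fugl-Meyer upper extremity score of at most 58 out of 66 and active wrist and thumb movement. Nothing refers to walking, yet section 10.0 words the walking tests as applying to participants generally.
6. **Risk (section 15.0).** This is the only other place where the walking tests appear. The precautions in sections 10.0 and 15.0 are real: a ceiling-attached harness for all treadmill walking, a therapist or assistant alongside, self-limited speed, rest on request, and vital signs at least every five minutes of activity. Overground, ceiling support is used only where feasible. The protocol itself still counts falls and injury as a remaining risk.

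MRI and actigraphy are also missing from the section 4.0 prose, so absence there proves little alone. What sets the walking tests apart is that they are missing from all three columns.

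**The case against.** The strongest reply is that section 4.0 is not a closed list. It introduces the scales as included outcomes, sends the reader to the design section for detail, and refers to a table that does not follow it in the text available here. The walking tests are in the design section, with a purpose of sorts: speed, step size and adaptability. They recur in the risk section, so they look deliberate. Section 17.0 foresees sharing data with a stroke registry, and the analysis of exploratory measures can be left to an SAP.

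Part of this stands. Section 4.0 cannot show that gait has no role, and declared exploratory data would be legitimate. But the design section gives the walking tests no aim and no time point, the schedule omits them, and section 17.0 names no gait measure. Which procedures are done, why, and at which visits is protocol content.

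The safeguards also count. They reduce the risk, and the treadmill harness is described as preventing a fall. They do not remove a risk that section 15.0 itself acknowledges.

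A reader might infer that people who cannot walk would be made to do treadmill tasks. The documents do not say so. Section 12.0 describes a phone screen for conditions that put a participant at risk, physical assistance is provided, and the separate screening form is not shown. What can be said is that the eligibility text and the walking procedure do not refer to each other.

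**Conclusion.** The point holds as an inconsistency with a cost to participants. Two procedures, in up to 20 people, carry an acknowledged fall risk and some burden, and serve none of the stated aims, named endpoints or scheduled assessments. It merits an amendment but does not affect the analysis of any named endpoint. The conclusion assumes that the schedule table is complete as it appears and that no separate document assigns the tests a purpose and visits.

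Two stronger readings are not supported:

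- A reader might infer that fatigue from walking adds noise to the arm outcomes. The protocol fixes no timing for the walking tests, so nothing places them close to the arm assessments, and nothing in it says that such fatigue alters arm scores.
- A reader might quote the event rate that one fall would produce among 20 participants. That fraction holds for any single event and says nothing about how likely a fall is. Nor do the documents suggest that the investigators or the DSMB could not recognise a fall in a supervised walking test for what it was.

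**What to change.** Reconcile sections 4.0, 5.0, 10.0 (procedures and schedule table) and 15.0 in one of two ways.

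- **Remove** the overground and treadmill tests from Aim 2, with their risk paragraph. This takes a short amendment and reduces risk and burden. The downside is the loss of exploratory gait data that no stated aim uses.
- **Keep** them as a declared exploratory measure. State the purpose and the variables recorded in section 4.0, add baseline and end-of-treatment visits to the schedule, and bring the eligibility text and the walking procedure into agreement. What any such eligibility text should require is a clinical matter for the sponsor. Tabulate adverse events from the walking tests separately from those of taVNS and task-specific training, because safety is part of the primary goal. This costs a few lines of text and one extra category in the safety tables; the burden and the residual risk remain, but for a stated reason.

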Multiple Interleaved taNS/fMRI scan will be carried out each visit using a gradient echo-based echo-planar imaging (EPI) scan sequence. Biphasic electrical pulses (Current = 200% perceptual threshold; Pulse width = 500µs; Frequency = 25Hz) generated by a Digitimer DS7AH (Digitimer Ltd, Hertfordshire, England) located just outside of the scanner room will be delivered to a special non-ferromagnetic Ag/AgCl clip electrode via a 7-m shielded copper cable. The cable will enter the scanner room through a wave guard. A 100kΩ resister will be placed in series to the stimulating electrode to prevent artificially induced currents from the MRI scanner interacting with the cable and the ear electrodes.

Interleaved taVNS/fMRI pulses will be delivered to the same left tragus or earlobe location as conducted in Aim 1. E-Prime 2 software (Psychological Software Tools, Inc.; Sharpsburg, PA) will be used to trigger a series of tVNS pulses in a block design every 10th TR for exactly 10 TRs (e.g. stimulate during TRs 10-20, 30-40, 50-60, 70-80, 90-100, 110-120) in the scan sequence. A total of 6 interleaved stimulation blocks will be delivered over 8-10 runs. The entire scanning sequence should last less than an hour.

Task-specific training (motor rehabilitation)

All participants enrolled in the pilot dosing trial will receive TST by a trained therapist in the **QBAR CORE**. TST will be administered 3 times per week for 4 weeks (12 total sessions). Each session will last 1 hour, and participants will be connected to EMG electrode arrays that will sense movements while the affected limb is trained in functional tasks like reaching forward to hold a glass and drinking from it, picking up and using objects, fine motor task and dexterity training. During TST, taVNS will be delivered in a movement-gated fashion.

Collected Measures :

MRI: Participants will attend 2, 1-hour fMRI scans (baseline & post-treatment 18) at the MUSC Center of Biomedical Imaging [name] (**Part of the NI Core**). During these neuroimaging sessions, we will collect high resolution T1 structural scans, fMRI BOLD during sequential finger-tapping task (thumb to fifth finger) both paretic and nonparetic hands, followed by the concurrent taVNS/fMRI paradigm (lesioned and contralesional ear targets) developed by [name] here at MUSC.

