Daily Life Activity Improvement Using Actigraphy: At-home upper limb motor activity of both the paretic and nonparetic limb will be collected using 2 independent actigraphy monitors (ActiGraph, Pensacola, FL), one on each arm, during the treatment phase of this trial. We will assess overall activity of upper limbs, as well as the ratio of activity of the paretic vs non-paretic arms.

Estimated Difficulties, Limitations and Time Frames

Estimated Difficulties. Many of the potential problems will manifest in the development of determining optimal EMG Quantification thresholding in chronic stroke patients in AIM 1. Although our lab is very experienced and we have resolved this type of scientific problem in the past with the administration of closed-loop TMS in the Brain Stimulation Lab.

Limitations. There are two potential limitations with these studies. The first is tolerability of electrical nerve stimulation of the tragus and earlobe. Although we do not anticipate any issues, drop-out may be an issue due to discomfort of the stimulation. If discomfort occurs we will decrease stimulating current amperage.

Estimated Time Frames. We plan on completing Aim 1 within 3 months. Specific Aim 2 will take approximately 18 months to complete (20 individuals attending rehabilitation training programs, with about 3 participants recruited every 3 months).

	Treatment Day					F/U Week	
	0	3	6	9	12	2	8
MRI	X				X		
Clinical Assessment	X	X	X	X	X	X	X
Kinematics	X				X		
Take-Home Actigraphy	Utilized During Treatment Phase					X	X

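### Actigraphy is presented as a measure of daily-life improvement, but no wear period before the first treatment session is defined, so change has no clean starting point

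*Protocol*

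**What the plan says.** The actigraphy paragraph of Protocol section 10.0 is headed "Daily Life Activity Improvement Using Actigraphy". Two monitors are worn at home, "one on each arm, during the treatment phase of this trial". Two quantities are named: "We will assess overall activity of upper limbs, as well as the ratio of activity of the paretic vs non-paretic arms". No reference period is given for either.

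In the schedule table at the end of section 10.0, the actigraphy row has a single entry under the treatment-day columns, "Utilized During Treatment Phase", followed by marks at follow-up weeks 2 and 8. The paragraph does not mention wear at follow-up.

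The other three rows (MRI, clinical assessment, kinematics) each carry a mark at day 0. For kinematics the text also states the reference, since it will "quantify functional improvements comparing post-treatment kinematics to baseline". For MRI the text plans two scans, one at baseline and one after treatment.

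**The concern.** Improvement is a change from a starting state. If recording begins only once training has begun, the earliest actigraphy value may already include some effect of training or of stimulation. Two things are then at stake.

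- **Size of the change.** Any gain made before or during the first recording period is subtracted from the estimate.
- **Precision and balance between arms.** Section 12.0 gives 10 participants per cell. In groups that small, chance differences in starting arm use can matter, and the best covariate for later actigraphy is usually the same measure taken before treatment. An early-treatment value is a poor substitute, because adjusting for it can remove part of the effect being estimated.

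This is a matter of what is recorded. A statistical analysis plan can choose covariates and contrasts, but it cannot supply a recording that was never made. It matters somewhat more here because section 12.0 makes the determination of effect sizes for a follow-up proposal one of the primary goals, and its power paragraph refers to changes in activity level.

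**Working it through.** **1. The schedule, row by row (section 10.0)**

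| Measure | Day 0 | Reference for change stated in the text |
|---|---|---|
| MRI | marked | baseline and post-treatment scans |
| Clinical assessment | marked | weekly series that includes day 0 |
| Kinematics | marked | post-treatment compared with baseline |
| Actigraphy | one entry for the treatment phase | none |

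Actigraphy is the only row with neither a separate day-0 mark nor a stated reference.

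**2. Does the limb ratio supply a reference?** The ratio of paretic to non-paretic activity compares two limbs over the same period. It is not a value from an earlier time. The kinematics paragraph treats the two as different things: it lists comparison with baseline and, separately, comparison between limbs.

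**3. The nearest figure in the plan.** Section 12.0 cites 20 per group for changes in activity level at d = 0.8 and 80% power. With n per group = 2(z_α + z_β)²/d²:

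- one-sided 0.05: 2(1.645 + 0.842)²/0.64 = 19.3, so 20;
- two-sided 0.05: 2(1.960 + 0.842)²/0.64 = 24.5, so 25 (26 with the t distribution).

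The cited figure reproduces only as a one-sided test; the protocol does not state sidedness. It gives the scale for step 4 and does not itself bear on the missing baseline.

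**4. Possible attenuation (illustration; the shares are assumed).** Suppose a share f of a true between-arm gain of d = 0.8 is already present in the first recording period and change is measured from that period, with the standard deviation held fixed. The measurable effect is 0.8(1 − f). Two-sided power with n = 10 per cell is about Φ(d√(n/2) − 1.96), where √(10/2) = 2.236.

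| f | measurable d | approximate power |
|---|---|---|
| 0% | 0.80 | 43% |
| 12.5% | 0.70 | 35% |
| 25% | 0.60 | 27% |
| 50% | 0.40 | 14% |

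The t distribution gives about 40% instead of 43% in the first row. The documents give no figure for f. The loss applies to change from early wear; a comparison of late values alone would not lose the share f, but would have no baseline on the same measure.

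**5. What baseline adjustment could be worth (the correlation r is assumed).** Adjusting for a covariate with correlation r leaves 1 − r² of the variance.

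- r = 0.7: 1 − 0.49 = 0.51 remains, so 49% is removed; 1/0.51 = 1.96.
- r = 0.9: 1 − 0.81 = 0.19 remains, so 81% is removed; 1/0.19 = 5.26.

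These ratios compare adjustment with no adjustment at all. If a day-0 proxy has correlation q with later actigraphy, replacing it by baseline actigraphy changes the variance by a factor (1 − q²)/(1 − r²). This is below 1/(1 − r²) for any q other than zero. The documents give neither q nor r.

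**The case against.** The strongest case on the other side has four parts.

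- **The table entry may cover day 0.** It stands under columns running from day 0 to day 12, and with 12 sessions planned, day 0 may well precede session 1. A missing separate mark is what a spanning cell looks like, so a reader should not infer that the table rules out wear on day 0. This stands. Even so, the entry refers to the treatment phase, and at-home activity accumulates over days. No interval between hand-out and session 1 is set, so the starting value is undefined at best.
- **Change can still be estimated.** A reader might infer that improvement cannot be estimated at all. The documents do not support that. Change from early to late treatment, and to follow-up weeks 2 and 8, remains available in both quantities. What is lost is a secure link to the pre-treatment state.
- **Baseline covariates exist.** A reader might infer that comparisons between arms must go unadjusted for starting arm use. They need not: the Motor Activity Log and three motor scales are scheduled at day 0, and whether to use them can be left to the analysis plan. They are proxies, however, and not the same measure.
- **The gain is easily overstated.** The ratios of about 2 and 5 in the working might be read as a gain in effective sample size. They rest on assumed correlations and on no other adjustment, and the protocol states no between-arm actigraphy test to which they would apply. Nor do the documents show how widely starting arm use varies. Section 5.0 admits Fugl-Meyer scores up to 58 but also requires active wrist and thumb movement, which limits the severe end.

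It is also true that section 4.0 does not list actigraphy among the endpoints and that the trial is an exploratory open-label pilot. That lowers the severity; it does not supply the missing starting value.

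**Conclusion.** The point holds in a limited form. The protocol calls actigraphy a measure of improvement but defines no recording before the first treatment session, and its text and table disagree on wear at follow-up. Improvement from the pre-treatment state may be understated by an amount the documents do not allow one to calculate. Later actigraphy can be adjusted for proxies at baseline, but not for itself. The 49% to 81% reduction in variance depends on the assumed correlation of 0.7 to 0.9 and is an upper guide, since it ignores what the day-0 scales would already explain. The gap itself does not depend on any assumed number. Severity is low to moderate: no listed endpoint rests on this measure, but the gap cannot be repaired after the data are collected.

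**What to change.** - Hand out both monitors at the baseline visit for a short wear period of stated length, the same in both arms, ending before session 1.
- Mark that period separately in the actigraphy row of the schedule table.
- Name it as the reference, and as the covariate, for change in overall upper-limb activity and in "the ratio of activity of the paretic vs non-paretic arms".
- Align the paragraph with the table on follow-up weeks 2 and 8.

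The same devices are used a few days earlier, so the cost is a few extra days of wear for each participant. If a pre-treatment period is not feasible, the minimum is to drop the word improvement from the heading and state which recording period serves as the reference.
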